1 STUDY SYNOPSIS

Complete Protocol Title	Anaverse [™] Glenoid System and its instrumentation - Retrospective and Prospective, Non-Controlled Post Market Clinical Follow-Up Study
Protocol Number	CME2017-11E
Short Protocol Title	Anaverse [™] Glenoid System and its instrumentation
Sponsor	Zimmer GmbH, [name]
Manufacturer	Zimmer Switzerland Manufacturing GmbH, [name]
Study Device(s)	Anaverse [™] Glenoid System
Study Objectives/Endpoints	The objectives of this study are to confirm safety, performance and clinical benefits of the Anaverse™ Glenoid System and its instrumentation by analysis of standard scoring systems, radiographs and adverse event records. The safety of the system will be assessed by monitoring the frequency and incidence of adverse events. The performance and clinical benefits will be evaluated by assessment of the overall pain and functional performance, survival, and radiographic parameters of all enrolled study subjects. The primary endpoint is defined by the survival of the implant system at 2 years which is based on removal or intended removal of the Anaverse™ Glenoid System baseplate and will be determined by using the Kaplan Meier method.
Indications/Target Population	Patients suffering from severe shoulder pain and disability indicated for implantation of the Anaverse™ Glenoid System in cases of total shoulder arthroplasty in reversed configuration. Patients who underwent total shoulder arthroplasty conversion from anatomical to reversed will be enrolled for subgroup analysis. Patients must meet all inclusion and none of the exclusion criteria. The reversed configuration of the Anaverse Glenoid System is indicated for patients with significant shoulder disability due to gross and irreparable rotator cuff deficiency. A functional deltoid muscle is necessary to use the device. The conversion from anatomical to reversed configuration is indicated for patients that were implanted with the system in the anatomical configuration and that present irreparable rotator cuff and superior migration of the humeral head, leading to a reduction in sub-acromial space.
Inclusion/Exclusion Criteria	Inclusion and exclusion criteria reflect indications and contraindications reported on the device instructions for use (IFU).

Inclusion criteria:

- Patient is 18-75 years of age, inclusive.
- Patient is skeletally mature.

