	of the Investigator place the patient at undue risk or interfere with the study. Patient is known to be pregnant or breastfeeding. Patient is a vulnerable subject (prisoner, mentally incompetent or unable to understand what participation to the study entails, a known alcohol or drug abuser, anticipated to be noncompliant). Patient has any physical conditions that would impair adequate implant support and/or prevent the use of an appropriately sized implant. Patient has any sign of infection (affecting the shoulder joint or in its proximity). Patient has glenoid presenting with large defects due to erosion, which would lead to insufficient bony support or malalignment of the devices. Patient is skeletally immature. Patient has any sign of neuromuscular compromise (excluding rotator cuff tear). Patient has vascular deficiency in the affected limb in sufficient degree to endanger the success of the intervention. Patient has absence of musculo-ligamentous supporting structures. Patient suffers from joint neuropathy or other conditions that may lead to inadequate skeletal fixation. Patient has significant injury to the upper brachial plexus. Patient has non-functional deltoid muscle. Specific exclusion criteria for Conversion from Anatomical to Reversed Configuration: Unstable fixation of Baseplate after removal of PE Liner. Superior tilt of Baseplate exceeding 15° compared to scapular axis Superior malposition of the Baseplate which would prevent correct assembly of the Glenosphere. Evidence of mechanical or fixation failure of the Baseplate, TM Pegs or DPSC Screws, obtained pre- or intra-operatively, which would compromise the success of the conversion surgery.
Study Design	Retrospective and prospective, non-controlled post market surveillance study.
Clinical Phase	Post-market
Sample Size	30 shoulders.

	2
Length of Study	3 years (1 year of enrollment plus 2 years of follow-up): follow-up visits at 6 weeks, 1 and 2 years postoperatively.
Materials and Methods	Case report forms will be completed either in-office or hospital at Pre-op, Surgery, Discharge, and at the 6 weeks, 1 year, and 2 year post-operation intervals.
Data Collection	Paper/Electronic

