Statistical Reporting	Data collected will be summarized and reported to each participating investigator. Statistical analysis will be conducted by Zimmer Biomet or its designee. Survivorship will be evaluated using Kaplan-Meier. Categorical data, such as incidences and device-related complications, will be summarized using counts and percentages with 95% confidence intervals. Continuous data, such as patient satisfaction scores, will be summarized by using means, medians, standard deviations, minimum, maximums, and 95% confidence intervals. Patient demographics, such as age and gender, will also be similarly summarized and reported on. Patients who underwent reoperations and/or revisions of components other than the baseplate will also be included in the statistical analysis. This subpopulation is not statistically powered; however, it will be included in the statistical analysis. Statistical analyses will be performed using SAS 9.4. The binomial distribution tests will have 80% probability of computing a two-sided 90% confidence interval on survivorship of each device with a non-inferiority margin of 0.09.
Scores/Performance Assessments	Constant-Murley, Patient Satisfaction, Revisions, Adverse Events, Radiographic Assessment.
Standards	 The PMCF is compliant with the below: ISO 14155: 2020 - Clinical investigation of medical devices for human subjects - Good clinical practice. The Declaration of Helsinki (DoH) – Ethical principles for medical research involving human subjects. European Regulation (EU) 2017/745.
Study Funding	Funding for this clinical study is made available by Zimmer Biomet to support clinical data collection, IRB/EC review fees and other expenses associated with the conduct and execution of this study protocol as outlined in the fully executed Clinical Trial Agreement

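### Device-related complications are summarised as crude percentages with no stated denominator and no handling of incomplete follow-up, so once any shoulder is lost the figure can misstate the 2-year incidence in either direction

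*Combined protocol and SAP*

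**What the plan says.** All the relevant text is in section 1, Study Synopsis.

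- **Study Objectives/Endpoints**, on safety: "The safety of the system will be assessed by monitoring the frequency and incidence of adverse events". On the primary endpoint: "The primary endpoint is defined by the survival of the implant system at 2 years", based on actual or intended removal of the baseplate.
- **Length of Study**: "3 years (1 year of enrollment plus 2 years of follow-up", with "follow-up visits at 6 weeks, 1 and 2 years postoperatively".
- **Statistical Reporting**, on survival: "Survivorship will be evaluated using Kaplan-Meier". On complications: "Categorical data, such as incidences and device-related complications, will be summarized using counts and percentages with 95% confidence intervals".
- **Sample Size**: 30 shoulders.

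The synopsis does not give an expected loss to follow-up, an expected complication rate, the denominator of the complication percentages, or a rule for shoulders with less than 2 years of observation. It does not name a 2-year complication incidence as a target of estimation.

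**The concern.** Kaplan-Meier lets a shoulder contribute for as long as it is observed. The plan uses it for baseplate survival but provides nothing equivalent for complications in the same shoulders over the same period. A complication in the second year cannot be counted in a shoulder last seen at 1 year. How that shoulder enters the percentage depends on the denominator, which is left open.

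Adverse-event incidence is how the study proposes to judge safety, and there is no control arm in which the same distortion would appear. With all enrolled shoulders as denominator, poorer follow-up lowers the reported complication rate. The accompanying 95% interval would also treat every shoulder in the denominator as fully observed. Because the choice is not fixed in advance, it could be made after the data are seen.

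**Working it through.** **Plan's own figure.** There is none to reproduce. The 30 shoulders and the power statement concern survivorship; nothing numerical is stated for complications.

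**Inputs.** From the synopsis: 30 shoulders, 2 years of follow-up, visits at 6 weeks, 1 and 2 years. Assumed, because the synopsis is silent: true 2-year risk R = 0.15, a fraction L = 0.20 lost independently of risk (0.30 also shown), and a constant hazard.

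**Expected percentage over all enrolled shoulders.** With hazard λ = −ln(1 − R)/2 and loss at time t (years),

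crude = (1 − L)·R + L·(1 − exp(−λt)).

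For R = 0.15, λ = 0.0813. At t = 1, 1 − exp(−λ) = 0.0780. At t = 6/52, it is 0.0093.

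| Loss | Lost after 1 year | Lost after 6 weeks |
|---|---|---|
| 20% | 0.80×0.15 + 0.20×0.0780 = 13.6% | 0.80×0.15 + 0.20×0.0093 = 12.2% |
| 30% | 0.70×0.15 + 0.30×0.0780 = 12.8% | 0.70×0.15 + 0.30×0.0093 = 10.8% |

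With 20% lost at 1 year the gap is 1.4 points, or 30 × 0.0144 = 0.43 of a shoulder.

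**Completers as denominator.** Here this means all observed events divided by shoulders that either had an event or reached 2 years. With 20% lost at 1 year: 0.1356/(1 − 0.20×(1 − 0.0780)) = 0.1356/0.8156 = 16.6%, above the true 15%. If events in shoulders that later dropped out were also removed, the expected value would return to 0.12/0.80 = 15%, but reported complications would be discarded.

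**Worked example.** 30 shoulders: 2 have complications before 1 year, 6 are lost event-free at 1 year, and 2 have complications later. After the first 2 events 28 remain event-free; after the 6 losses 22 are at risk.

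- All enrolled: 4/30 = 13.3%
- Kaplan-Meier: 1 − (28/30)(20/22) = 15.2%
- Completers: 4/24 = 16.7%

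**Sensitivity to event timing.** Suppose 70% of the 15% risk (10.5%) falls by 6 weeks and the other 4.5% is spread evenly to 2 years. The risk by 1 year is then 0.105 + 0.045×(1 − 0.115)/(2 − 0.115) = 12.6%. With 20% loss:

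- All enrolled: 0.12 + 0.20×0.105 = 14.1% (lost after 6 weeks) or 0.12 + 0.20×0.126 = 14.5% (lost after 1 year). The shortfall drops to 0.9 or 0.5 points.
- Completers, lost after 1 year: 0.1452/(1 − 0.20×0.874) = 17.6%. Early clustering does not help this version.

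**Wider range.** If loss is spread exponentially over the 2 years with rate μ = −ln(1 − L)/2, the expected all-enrolled figure is λ/(λ + μ)·(1 − exp(−2(λ + μ))). Over true risks and losses of 5% to 30%, it falls short by 0.1 to 4.5 points. At 10% risk and 20% loss it is 9.0%, against 11.1% with completers. With no loss, crude and Kaplan-Meier figures agree.

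**Against sampling error.** The exact 95% interval is 3.8% to 30.7% for 4/30, and 2.1% to 26.5% for 3/30.

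**The case against.** A reader might infer that lost shoulders will be counted as complication-free, so that the 2-year complication incidence is understated. The document does not support that. No denominator is stated, no loss rate is stated, and with completers as denominator the bias reverses. Planning Kaplan-Meier allows for censoring but does not predict how much there will be. The criteria require patients able to take part in follow-up and exclude those unable to comply with it, which may limit loss.

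The cohort also makes heavy early loss less likely. One inclusion criterion requires the operation to precede site initiation, so some follow-up may already have elapsed at enrolment. The figures for loss straight after 6 weeks are therefore an extreme case. A constant hazard enlarges the all-enrolled shortfall compared with events clustered early.

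Safety reporting is descriptive: no test or margin is attached to complications, and counts with percentages are a legitimate summary of a small series. No conclusion from 30 uncontrolled shoulders is likely to turn on one or two points. Finally, the document reviewed consists of the synopsis, and a fuller analysis plan might define the denominator.

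All of this stands as a limit on direction and size. It does not supply the missing definition: the same data can give 13.3% or 16.7% under the text as written.

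**Conclusion.** The concern holds in conditional form. The synopsis fixes neither the denominator nor the handling of incomplete follow-up for its complication percentages. If any shoulders are lost before 2 years, the all-enrolled figure is expected to be too low as an estimate of the 2-year incidence, and observed events over completers too high. With no loss there is no problem.

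Under the assumed 15% risk, 20% loss at 1 year and constant hazard, the gap is 1.4 points below the truth with all enrolled and about 1.6 points above it with completers. Both are small beside the width of the interval at 30 shoulders. Loss is assumed independent of risk; if it is related to complications, these figures do not apply. The primary endpoint is untouched. This is an inexpensive improvement to the safety summary, not a flaw that threatens the study's main result.

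**What to change.** Keep the counts and crude percentages and state their denominator. Add to Statistical Reporting text such as:

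> First device-related complication and first serious adverse event are each analysed as time from surgery to event. The 2-year cumulative incidence is estimated by the Aalen-Johansen method with a 95% confidence interval. Death is a competing event, as is baseplate removal where removal is not itself the event of interest. Shoulders without an event are censored at last contact. Numbers at risk are shown at 6 weeks, 1 year and 2 years.

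If no competing event occurs, this equals 1 minus Kaplan-Meier. Because surgery precedes enrolment for these patients, the text should also say how events and follow-up before enrolment are captured.

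The cost is one extra analysis. Last-contact dates are already needed for the primary Kaplan-Meier estimate; event onset dates must be recorded. No additional patients or visits are required.
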